### *External validation*

Our validation cohort has a fixed sample size of 336. To ensure unbiased and precise performance measures (e.g., calibration and discrimination), Collins et al. [73] recommend that external validation samples have a minimum of 100 events. We will adhere to this guideline when interpreting the results from the external validation.

### **Missing data**

[figure not shown]
We plan to perform a complete case analysis if <5% of the participants are excluded from the regression analyses due to missing data [37]. If >5% are missing, we will use multiple imputation by chained equations. Multiple imputation was chosen as an adequate method, as it avoids removing people from the study and is a suitable technique to deal with missing prognostic factor data [74]. We will create imputed datasets using the *mim* module in STATA. To reduce bias and increase the precision of the imputation, we will include auxiliary variables in the imputation model. Auxiliary variables are variables within the data that are not included in the analysis but are

highly correlated to the prognostic variables of interest [75]. To ensure reliable imputations across the imputed datasets, we will compare observed and imputed values by visual inspection (tables and plots). Using registry data, we do not expect missing data on the primary outcome (sickness absence days). Nevertheless, multiple imputation of the outcome will not be performed.

## Statistical analysis methods

### *Model development*

Considering the sample sizes of our data, we will develop the prognostic models based on the 'full model approach' (Figure 2). That is, using the pre-selected prognostic factors based on literature review and clinical grounds without any being excluded at a later stage [37]. This approach has several advantages compared to other selection methods (such as stepwise methods), as it avoids the risk of removing clinically important prognostic factors, reduces estimation bias and overfitting, and avoids the selection process to be overly data-driven [37,76,77].

**Figure 2.** Flow diagram of model development. Abbreviations: DP, disability pension; MSD, musculoskeletal disorder; RTW, return to work; WAA, work assessment allowance.

We will use multivariable logistic regression, since this method is recommended when the outcome is binary, and the independent variables are dichotomous, continuous, categorical or a combination [20,37]. Continuous variables will be kept continuous and not categorised to avoid losing prognostic information [78]. Nonlinear transformations will be checked using multivariable fractional polynomials using STATA package *mfp* (or *mfmp* for multiple imputation data) [79] or other methods for nonlinear modelling (e.g., splines or segmented regression).

### *Model performance*

The predictive performance of the apparent model in the development sample will be assessed using measures of overall performance, calibration, and discrimination. Overall performance will be assessed using Nagelkerke's pseudo  $R^2$ . Calibration will be examined by plotting (calibration plot) the observed proportions of events against the predicted risks for groups defined by ranges of individual predicted risks. To quantify the performance of calibration, the calibration will be described by calibration-in-the-large (intercept) and calibration slope, with perfect calibration characterised by an intercept of 0 and a slope of 1 [37]. We will also assess the ratio of Expected to Observed cases (E/O). To explore the model's ability to discriminate those at higher risk of having an event from those at lower risk, c-statistic will be used. The c-statistic is equivalent to the area under the curve (AUC) statistic from receiver operating characteristic (ROC) curves. An index measure of 1 indicates perfect discrimination, whilst 0.5 demonstrates that the discrimination of the model is no better than by chance alone [37]. A c-statistic of 0.60–0.69 represents poor discrimination, 0.70–0.79 fair, 0.80–0.89 excellent, and  $\geq 0.90$  outstanding discrimination [80].

To decrease the possibility of overfitting the model, the amount of optimism in the model will be assessed and corrected by internal validation techniques, using bootstrap re-sampling to estimate the degree of optimism due to overfitting [81]. To adjust for this overfitting, we will use the *bsvalidation* module in STATA or similar commands in STATA or R software. The bootstrap procedure will include all modelling steps for the assessment of the model's performance. The model building will be repeated for 500 bootstrap samples [82,83]. Initially, the difference in bootstrap performance and test performance will be averaged over the 500 samples. This will

give a single estimation of the optimism of the model. Finally, this estimate will be subtracted from the estimates of the apparent model performance.

After the optimism estimate has been subtracted from the model's performance, a new calibration plot will be performed to provide a shrinkage factor. This factor will be applied to all predictor effects in the apparent model to shrink for overfitting. A re-estimation of the intercept of the model will then be performed [21,37]. After these adjustments, the final apparent model is complete.

### *External validation*

We will externally validate the models to determine the validity of predictions for workers on sick leave outside the development sample. We will use data from the MI study, which included participants from a different geographical region than the development sample. Hence, this validation is called external geographic validation. External geographic validation has been found to have higher generalisability than internal validation and is essential before a prognostic model can be applied to practice [37,84].

To assess the extent of transportability or reproducibility, we will estimate the relatedness between the development and validation samples according to Debray et al. [85]. This will be performed using two approaches. In the first approach, we will examine relatedness of the samples by estimating a binary logistic regression model (membership model), to predict the probability that a participant belongs to the development sample ("1") compared with the validation sample ("0"). The independent variables in this model will include the primary outcome (long-term sickness absence), age, sex, education level, and all the predictors from the prognostic model. Thereby, we will assess the discriminative ability of this membership model by quantifying the *c*-statistic. Low values (close to 0.5) indicate that the samples are largely the same and that the case-mix is indistinguishable between the datasets. In the second approach, we will compare the mean and standard deviation of the linear predictor of the prognostic model in the development and validation sample. A large difference in the linear predictor indicates a heterogeneity of the case-mix between the two samples.

Model performance will be tested in the external validation sample using the predictive performance statistics calculated as detailed above in the model performance section. It will be estimated using the model coefficients from the developed models to calculate the individual risk scores [86]. In addition to these performance measures, we will also assess the clinical usefulness of the prognostic models by calculating decision-curve analysis for the model. This will evaluate the ability to make better decisions with a prognostic model than without, by using a decision-curve analysis that estimates the net benefit and compares this to decision-making strategies (treat all/treat none) [82,87].

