#### *Development sample*

To develop the models, we will combine data from a prospective cohort study [22] and an RCT (MI-NAV trial) [25]. The prospective cohort study was carried out from November 2018 to February 2020, involving workers on sick leave due to MSDs who were invited to participate through the electronic communication website of the Norwegian Labour and Welfare Service (NAV). The inclusion criteria were workers aged 18 to 67 years on sick leave for a minimum of 4 weeks with a diagnosis within the musculoskeletal (L) chapter of ICPC-2 (International Classification of Primary Care, Second edition) [26]. Exclusion criteria were insufficient Norwegian or English

language skills to participate in the study. This study recruited 549 participants with median age of 50.1 (interquartile range [IQR], 41.9-56.9) years, who had been on sick leave at a median of 37.8 (IQR, 26.1-80.3) workdays the year prior to the baseline assessment.

The MI-NAV trial was a multi-arm randomised controlled trial investigating the effectiveness of adding motivational interviewing or stratified vocational care intervention to usual care in a sample of workers on sick leave due to MSDs. The inclusion criteria in this trial were similar to the prospective cohort study: participants were eligible if they were aged 18-67 years, employed full or part-time, and on sick leave due to MSDs (L-chapter of ICPC-2) for at least 50% of their contracted work hours for more than 7 weeks. Exclusion criteria included serious somatic or mental health disorders, pregnant women, those who were unemployed, freelancers, self-employed workers and people lacking sufficient Norwegian or English language skills. This trial consisted of 514 participants, median age 48.8 (IQR, 40.8-55.3) years, who had been on sick leave at a median of 36.8 (IQR, 29.3-50.0) workdays the year prior to the baseline assessment. The MI-NAV trial showed a 7-day non-statistically significant reduction in sickness absence over 6 months for the intervention groups compared to usual care.

**Table 1.** Characteristics of the datasets that will be used in this study.

Study	N	Study type	County, Country	Diagnosis coding	Follow-up time	Inclusion criteria	Linkage to sickness absence registry data	Intended use of database
Prospective cohort study [22]	549	Prospective cohort	All counties, Norway	ICPC-2	12 months	Sick leave due to MSD for at least 4 weeks. Aged 18-67 years.	Yes	Development

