MI-NAV trial [25,27]	514	Three-arm parallel RCT	Vestfold, Norway	ICPC-2	12 months	Sick leave due to MSD for at least 7 weeks (>50 % of contracted working hours). Aged 18-67 years.	Yes	Development
MI study [24]	865	Three-arm parallel RCT	Trøndelag, Norway	ICPC-2	12 months	Sick leave due to any diagnoses for at least 8 weeks (>50 % of contracted working hours). Aged 18-60 years.	Yes	External validation

Abbreviations: ICPC-2, International Classification of Primary Care 2nd version; MI, motivational interviewing; MSD, musculoskeletal disorders; RCT, randomised controlled trial.

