### *Validation sample*

We will externally validate the models using data from all arms of a second RCT (MI study) [24]. This study evaluated the effect of motivational interviewing on return to work in a social security setting using a parallel group design. Participants aged 18 to 60 who had been on sick leave for more than 8 weeks were recruited through the NAV system. Individuals who were not employed or pregnant were excluded. This trial comprised 865 participants, median age 45.0 (IQR, 37.0-52.0) years, who had been on sick leave at a median of 52.1 (IQR, 40.4-65.6) workdays the previous year. The results from this trial have not been published yet.

The inclusion criteria for all studies are pragmatic and unrestricted, indicating that they are likely to be representative of the target population. We plan to use data from all arms (intervention and control) of the RCTs.

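### The external validation is only partly geographic, has no data for weeks 4 to <8 of the 4-12 week window, and is likely to be imprecise for WAA/DP

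*SAP*

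**What the plan says.** **Region.** The External validation section under Statistical analysis methods says that the MI study, "which included participants from a different geographical region than the development sample", makes the validation geographic. In Table 1 the development cohort is listed under "All counties, Norway", the MI-NAV trial (also development) under "Vestfold, Norway", and the MI study under "Trøndelag, Norway".

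**Time and age.** Objectives, Source population and Start-point all place prediction in weeks 4-12 of a sick leave spell, and Source population excludes anyone above 12 weeks at baseline. Both development studies enrolled ages 18-67. For the MI study, Table 1 gives "Sick leave due to any diagnoses for at least 8 weeks" and the Validation sample section says "Participants aged 18 to 60 who had been on sick leave for more than 8 weeks were recruited".

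**Size.** The External validation paragraph under Sample size fixes the validation sample at 336, cites a guideline of at least 100 events, and undertakes to follow it when results are interpreted. The readable text gives no validation event count for any outcome (Figure 1 is not shown). The sections on validation and model performance mention no confidence intervals.

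**The concern.** The SAP treats geographic external validation as a condition for using a model in practice, and its Discussion promises externally validated models, with an online calculator if performance is good. A reader would take this to mean two things: that the models were tested in a region that contributed nothing to their development, and that the test spans the intended 4-12 week window. The first is only partly true, and the second is not true for weeks 4 to <8.

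The missing weeks matter because Start-point argues against waiting too long, so the untested part of the window is the early part. Sensitivity analysis 6 itself describes sick leave duration as an important prognostic factor, so performance at weeks 8-12 cannot simply be carried back to week 5. For the rarer outcomes, the validation may also be too imprecise to say whether a model performs well.

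**Working it through.** **Region.** The cohort recruited 549 people from all counties, a frame that contains Trøndelag. Neither document excludes Trøndelag residents from the cohort or from the development set. MI-NAV contributes 514 of the 549 + 514 = 1,063 recruited for development (48%, before eligibility is applied) and is regionally separate. The regional mix therefore differs between development and validation, but the two regions are not disjoint. The number of cohort members from Trøndelag is not given.

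**Weeks.** The intended window is 4-12. Entry to the MI study is at about 8 weeks (Table 1 and the text differ on whether exactly 8 counts), and the upper limit is 12. Their intersection is about weeks 8-12. MI-NAV enrolled after more than 7 weeks, so development data for weeks 4-7 come essentially from the cohort alone.

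Three planned analyses might seem to fill the gap:
- The relatedness analysis (membership model and linear-predictor comparison) describes case-mix but supplies no outcomes for the missing weeks.
- Sensitivity analysis 6 removes participants above 8 weeks and names no sample. In the validation sample it would leave almost nobody.
- Sensitivity analysis 8 widens the diagnoses, not the entry week.

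**Events.** The plan gives no validation event figure to reproduce. Its development minimum of 826 does follow from its printed inputs, 19 / [(0.9 − 1) × ln(1 − 0.185/0.9)] = 825.7, but this says nothing about validation. The printed rates reproduce for two outcomes: 161/934 = 0.172 and 101/934 = 0.108. For >90 days, 416/934 = 0.445, not the printed 0.403, so both are carried.

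The validation rate is unknown and may be higher because entry is later, so I assume a multiple k of the development rate. Expected events = 336 × rate × k:

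| Outcome | k = 1.0 | k = 1.5 | k = 2.0 | k needed for 100 |
|---|---|---|---|---|
| >90 days | 150 (135 at 0.403) | – | – | below 1 |
| >180 days | 58 | 87 | 116 | 1.73 |
| WAA/DP | 36 | 55 | 73 | 2.75 |

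The last column is (100/336) / rate = 0.298/0.172 and 0.298/0.108, using unrounded values. For WAA/DP at k = 2.0, the binomial probability of reaching 100 events is 0.0003. For >180 days the probability is 0.06 at k = 1.5 and 0.97 at k = 2.0.

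**Precision.** For an assumed c-statistic c = 0.75 and event proportion p, the variance is c(1−c)[1 + (n/2 − 1)(1−c)/(2−c) + (n/2 − 1)c/(1+c)] / [n²p(1−p)]. The 95% half-widths at k = 1.0 / 1.5 / 2.0 are:
- >180 days: 0.069 / 0.059 / 0.055
- WAA/DP: 0.084 / 0.071 / 0.063
- >90 days at development rates: 0.052-0.053

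For WAA/DP this gives 0.67-0.83 at k = 1.0 and 0.69-0.81 at k = 2.0. Both intervals run from the SAP's poor band to its excellent band. A Hanley-McNeil variance gives wider half-widths for WAA/DP (0.095 and 0.069).

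For the expected-to-observed ratio, SE(ln E/O) = √[(1−p)/(np)]. Intervals around 1 at the same three multiples are:
- >180 days: 0.79-1.26 / 0.83-1.20 / 0.86-1.16
- WAA/DP: 0.74-1.36 / 0.78-1.28 / 0.82-1.23

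Centring these on 1 assumes that predictions are calibrated at the assumed rate.

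**The case against.** The strongest reply is that little is hidden. Table 1 and the Validation sample section disclose the region, entry week and age limit. The SAP plans a relatedness analysis to judge transportability, and it does not claim that 336 is adequate but commits to the 100-event guideline in interpretation. No primary estimate changes. Much of this stands: the missing event counts and intervals are largely a reporting matter. What remains is that the geographic label conflicts with Table 1 and that no sentence limits the externally validated claim to the weeks actually observed.

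Several stronger readings are tempting but unsupported:
- *That the validation is not external.* It uses an independent trial, so it is. The overlap is one of sampling frames and may be small.
- *That previous-year sick leave shows the later entry, because 8 weeks × 5 = 40 workdays and the MI study's lower quartile is 40.4.* MI-NAV required more than 7 weeks (35 workdays), yet the SAP reports a "median of 36.8 (IQR, 29.3-50.0) workdays the year prior to the baseline assessment", with a lower quartile below 35. Weeks × 5 is therefore not a floor. The MI study figures also describe all 865 recruits with any diagnosis. The entry criteria alone establish the gap.
- *That weeks 4 to <8 at least have their own bootstrap evidence.* The bootstrap is pooled over the 934 and gives nothing specific to those weeks.
- *That the age gap is as serious as the week gap.* Upper quartiles of 56.9 and 55.3 years put fewer than a quarter of recruits in each development study at 61-67.

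**Conclusion.** The point holds. As written, the validation is external but not strictly geographic. It supplies no evidence for weeks 4 to <8, about half the calendar width of the intended window; the share of participants in those weeks is not given. It also has none for ages 61-67, a minor gap.

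WAA/DP is expected to fall short of the cited 100 events across the assumed range of 1.0 to 2.0 times the development rate. >180 days falls short unless its rate is at least 1.73 times that rate. >90 days clears 100 at the development rate under either reading of that rate. The region and week conclusions rest on the documents alone. The event and precision figures rest on the assumed multiples and, for the c-statistic, on an assumed value of 0.75. The documents do not support saying that the overlap is large or that the plan ignores the event guideline. This should be corrected because it changes what can be concluded, though not how the models are fitted.

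**What to change.** - Replace the term *external geographic validation* with *external validation in an independent trial with partial regional overlap*. If county is available, report the number of cohort members from Trøndelag and add one sensitivity refit without them, keeping the 934 as the primary development set.
- Limit the externally validated claim, in the Discussion too, to about weeks 8-12 and ages 18-60. State that weeks 4 to <8 have no external evidence and only pooled internal validation.
- Specify that sensitivity analysis 6 is run in the development sample and reports optimism-corrected performance for participants at 8 weeks or less.
- Report validation events per outcome and a 95% confidence interval for every validation measure. Treat the WAA/DP validation as imprecise, and that for >180 days too if it has fewer than 100 events. If expected intervals for E/O are shown in advance, state that centring them on 1 assumes calibrated predictions at the assumed rate.

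The mismatch between 0.403 and 416/934 should also be corrected, but it is a separate point and does not alter this one.

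The cost is SAP wording, a narrower stated scope, routine reporting and at most one extra refit. No new participants are needed.

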### **Identification of candidate prognostic factors**

When developing a prognostic model, selection of candidate prognostic factors should be guided by evidence from the literature and consultations with content experts [37]. The included studies collected candidate predictors based on existing literature and expert knowledge using sociodemographic and clinical variables. The predictor data from the cohort and the MI-NAV study are nearly identical, but differ slightly from the MI study. For model development, we identified those prognostic factors that are available in all three datasets. Since the aim of our prognostic models is to predict

prolonged sickness absence with as good accuracy as possible, we included both modifiable and non-modifiable prognostic factors.

We identified a set of prognostic factors for the model development based on an iterative approach:

- 1. We identified candidate predictors of sickness absence from available literature:** The first author (TR) reviewed all available best-evidence synthesis of systematic reviews [28], systematic reviews [38–43], prognostic model studies [10–15,17,18,35,44–51], and expert opinions from Delphi-studies [52,53]. Additional focused searches on PubMed (<https://pubmed.ncbi.nlm.nih.gov>) for relevant prognosis studies were also conducted to identify additional evidence for candidate prognostic factors.
- 2. Clinical grounds through discussion in a multidisciplinary group:** The candidate prognostic factors from the literature review were shared with the research group, and through discussion we selected a set of prognostic factors to be used for model development, restricted to data availability and sample size calculation (see “Sample size” section).

The prognostic factors that were identified and that will be included in the model are summarised in Table 2. Because we will use data from randomised controlled trials, we must consider the extraneous trial effects which can limit the generalisability of the model validation [54]. Thus, we will model for treatment effect by following the guidance provided by Pajouheshnia et al. [54]. We will code the intervention predictor as a binary variable, to avoid overcomplicating the model.

**Table 2.** Summary of selected prognostic factors for model development with definition, variable type, unit/categories, measurement method, number of predictor parameters, and evidence.

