Prognostic factor	Definition	Variable type	Unit/categories	Measurement method	No. of predictor parameters	Evidence
Expectation of RTW	Expectation of probability of returning to work within 3 months	Continuous	0-10, 10 = best	Self-reported using item from ÖMPSQ-SF [55]	1	[14,17,28,40,52,56–63]
Pain intensity	Pain intensity last week	Continuous	0-10, 10 = worst	Self-reported	1	[17,38,43,52,53,61–65]

Depression/ anxiety	Self-reported depression or anxiety	Categorical	Recategorized from 5 to 3 categories	Self-reported using item from EQ5D [66]	3	[10,28,43,67]
Education level	Completed education	Binary	0 'Lower education: primary/secondary/voc ational school' 1 'Higher education: College/University. Recategorized from 4 to 2 categories	Self-reported	1	[10,13,14,18,2 8,44,45,52,53, 59]
Age	Age	Continuous	Years	Self-reported	1	[4,10,14,17,18 ,28,38–40,43– 46,52,53,56,5 8–63]
Previous sick leave	Days of sick leave previous year	Continuous	Days	Register data	1	[4,10,17,18,28 ,45,46,52,53,5 6]
Disability pension status	Receiving work assessment allowance or disability pension at starting-point	Binary	0 'No' 1 'Yes'	Register data	1	[4,10,17,18,28 ,45,46,52,53,5 6]
General health	Self-perceived general health	Continuous	0-100	Self-reported using VAS from EQ5D [66]	1	[10,18,40,44,4 5,52,53,61,62]
Fear- avoidance	Fear that movement or activity will worsen the injury	Binary	0 'No' 1 'Yes'	Self-reported using item from Keele STarT MSK tool [68,69]	1	[39,40,43,53]
Workability (job performance)	Self-reported current workability compared to at its best	Continuous	0-10, 10=best	Self-reported using item from Work Ability Index [35]	1	[18,35,44,46,5 2,53]
Intervention	Participant in a trial arm with an effective intervention	Binary	0 'No' 1 'Yes'		1	[70]
					Total 13	

[figure not shown]
Abbreviations: EQ5D, Euroqol questionnaire 5-dimensions; ÖMPSQ-SF, Örebro Musculoskeletal Pain Screening Questionnaire short form; RTW, return to work; SA, sickness absence; VAS, visual analogue scale.

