### Development

The sample size is fixed at 934 participants in the development sample. To adequately power the regression analysis and potential exploratory analysis, we will follow recent sample size recommendations by Riley et al. [71,72] using the *pmsampsize* module in STATA 16.1 (StataCorp LLC, Texas, USA). This prediction sample size calculator is also available online: <https://riskcalc.org/pmsamplesize/>.

In order to include all prognostic factors, corresponding to Table 1 and including 2 parameters for each continuous predictor to account for potential non-linear trends, 19 parameters ( $P$ ) are needed. We will target an expected shrinkage factor ( $S$ ) of 0.9, to

reflect small optimism in predictor effect estimates, as recommended by Riley et al. [72]. We assume that the models will have a modest Nagelkerke's  $R^2$  of 25% which corresponds to a Cox-Snell  $R^2$  of 0.185.

- For the first end-point (>90 days), the event rate is 0.403 (416 events of 934), which gives a minimum required sample size ( $n$ ) of 826 (with 368 events), resulting in an event per predictor parameter (EPP) of 19.35.
- For the second end-point (>180 days), the event rate is 0.172 (161 events of 934), which results in a minimum required sample size ( $n$ ) of 826 (with 143 events) and an EPP of 7.48.
- For the third end-point (WAA/DP), the event rate is 0.108 (101 events of 934), which gives a minimum required sample size ( $n$ ) of 826 (with 90 events) and an EPP of 4.7.

Our fixed sample size exceeds these minimum requirements. Therefore, we expect our study to be adequately powered which will lead to minimal shrinkage and reliable results.

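### The membership model includes the Intervention predictor, so trial allocation can make the development and validation samples look less related in case-mix than they are.

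*SAP*

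**What the plan says.** The SAP's External validation section (under Statistical analysis methods) sets out two checks of relatedness, intended to show whether validation tests reproducibility or transportability.

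- **Membership model.** A logistic regression predicts whether a participant belongs to the development sample. Its covariates are the primary outcome, "age, sex, education level, and all the predictors from the prognostic model". The reading rule is: "Low values (close to 0.5) indicate that the samples are largely the same and that the case-mix is indistinguishable between the datasets".
- **Linear predictor.** The second check is to "compare the mean and standard deviation of the linear predictor of the prognostic model in the development and validation sample", with a large difference taken as heterogeneous case-mix.

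Table 2 lists Intervention among the predictors with one parameter, defined as "Participant in a trial arm with an effective intervention". The text before the table says: "We will code the intervention predictor as a binary variable, to avoid overcomplicating the model". Under the full-model approach no predictor is dropped later. Neither check makes an exception for Intervention.

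**The concern.** Case-mix means the characteristics of the workers. Intervention records what a study did to them, and its distribution follows from design. Nobody in the observational cohort was in a trial arm, so that part of the development sample is coded 0 throughout. Every validation participant comes from a three-arm trial, and all arms are used. The share coded 1 can therefore differ between the samples even if the workers are exchangeable, and the membership model will use that difference to tell the samples apart.

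What is at stake is interpretation. A raised c-statistic would suggest that validation took place in a different population, and that reading colours how good or poor external performance is explained. With Intervention included, the reported c cannot separate a real difference, such as longer sick leave at entry, from allocation.

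**Working it through.** **1. Is Intervention counted as a model predictor?** Table 2 sums to 13 parameters, Intervention included. The Development sample-size section allows two parameters for each continuous predictor. There are six: return-to-work expectation, pain, age, previous sick leave, general health and workability. So 13 + 6 = 19, matching "19 parameters ( $P$ ) are needed". With shrinkage S = 0.9 and Cox-Snell R² = 0.185, n = P / [(S − 1) ln(1 − R²/S)]:

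- P = 19: 19 / (0.1 × 0.2301) = 825.7, so 826, the SAP's figure.
- P = 18 (Intervention left out): 782.2, so 783, which does not match.

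Intervention is in the model, and hence in both checks.

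**2. Share coded 1 in development.** The sample is 934, drawn from 549 cohort and 514 MI-NAV participants before the eligibility filter. The MI-NAV part is at least 934 − 549 = 385 (41%) and at most 514 (55%). Assume 1:1:1 allocation and two of three MI-NAV arms coded 1:

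- lowest: 385 × 2/3 / 934 = 0.27
- proportional split: (514/1063) × 2/3 = 0.32
- highest: 514 × 2/3 / 934 = 0.37

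**3. Membership c from Intervention alone, workers otherwise identical.** For one binary covariate, c = 0.5 + |p_dev − p_val| / 2.

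| MI study arms coded 1 | p_val | c for p_dev 0.27 to 0.37 |
|---|---|---|
| two of three | 0.67 | 0.65 to 0.70 |
| one of three | 0.33 | 0.50 to 0.53 |
| none | 0 | 0.64 to 0.68 |

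If only one MI-NAV arm is coded 1 (p_dev 0.14 to 0.18) and two validation arms are, c is 0.74 to 0.77.

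**4. Full membership model, by simulation.** 934 against 336, twelve other covariates with the same distribution in both samples, plus the outcome.

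| p_dev | p_val | apparent c with Intervention | without |
|---|---|---|---|
| 0.32 | 0.67 | 0.70 | 0.56 to 0.57 |
| 0.27 | 0.67 | 0.72 | 0.56 to 0.57 |
| 0.37 | 0.67 | 0.68 | 0.56 to 0.57 |
| 0.32 | 0.33 | 0.57 | 0.56 to 0.57 |

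The value near 0.56 without Intervention reflects overfitting of the membership model. At p_dev 0.32 the artefact is therefore about 0.70 − 0.56 = 0.14, not the whole distance from 0.5.

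**5. If the workers really do differ.** With p_dev 0.34, p_val 0.67 and an assumed true difference in one covariate, adding Intervention moves c from 0.71 to 0.77, or from 0.75 to 0.80 for a larger difference. With no true difference it moves from 0.56 to 0.69. With no validation arm coded 1, the move is from 0.71 to 0.81.

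**6. Linear predictor.** The mean shift is ln(OR) × (p_val − p_dev). The SAP gives no odds ratio, so 0.9 to 0.6 is assumed. With shares 0.32 and 0.67 and a simulated linear-predictor SD of about 1.15 to 1.18:

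| OR | mean shift (simulated) | in SD units |
|---|---|---|
| 0.9 | −0.04 | 0.03 |
| 0.8 | −0.08 | 0.07 |
| 0.6 | −0.19 | 0.16 |

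The SD itself hardly moves (1.166 against 1.161 at OR 0.8). With Intervention held at one value, the mean shift is about zero.

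**The case against.** The best case against runs as follows.

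- **The size rests on shares the plan does not give.** With one of three validation arms coded 1, nothing visible happens. Read literally, an effective arm may not exist: the MI-NAV effect was a non-significant 7 days and the MI study is unpublished. If no arm in either sample is coded 1, the variable is constant and drops out. This stands, and it is why a range is shown. It is also a reason to settle the matter now, since otherwise the artefact depends on a later coding decision.
- **Identical case-mix is hypothetical.** The sources differ in minimum sick leave (4 and 7 weeks against 8), upper age limit (67 against 60) and median prior sick leave (37.8 and 36.8 workdays against 52.1, before filtering). This stands: step 5 shows that the distortion is diluted, though not removed.
- **No rule hangs on the result.** The SAP sets no cut-off for c and no action. Calibration, discrimination and decision-curve results do not change. This stands and limits the point to interpretation.
- **Modelling treatment is deliberate.** It is, and nothing here argues against keeping Intervention in the prognostic model. That reason does not extend to counting it as case-mix.

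A reader might infer that the two samples would look unrelated, or that both checks are compromised. Neither follows. Values of 0.65 to 0.70 fall at or near what the SAP's own scale calls poor discrimination, and the linear-predictor shift is too small to count as a large difference. That poor performance would be excused as case-mix is conjecture.

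**Conclusion.** The point holds for the membership model. As written, it includes a variable fixed by design and reads the result as case-mix. If two MI-NAV arms and either two or none of the validation arms are coded 1, otherwise identical samples could look less related than they are, with an apparent c of about 0.7 in place of about 0.56. If one validation arm is coded 1, the effect is negligible.

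This rests on 1:1:1 allocation surviving the eligibility filter and on which arms are coded 1; the SAP states neither. For the linear predictor the effect is minor: at most about 0.16 SD in the mean at shares 0.32 and 0.67, for odds ratios no stronger than 0.6. It is worth correcting before analysis because the remedy is nearly free, but no coefficient or performance estimate is at risk.

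**What to change.** 1. Leave Intervention out of the membership model used to judge case-mix. Keep the outcome, age, sex, education and the other predictors as planned.
2. Report the share coded 1 in each sample, and state which arms are coded 1.
3. As a minor addition, report the mean and SD of the linear predictor with Intervention held at one common value in both samples, beside the planned version.

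The cost is a sentence or two in the SAP and one extra line of analysis. No data are needed and no information on case-mix is lost. One small residue remains: allocation can affect the outcome, which stays in the membership model. In the simulation this was negligible; at shares 0.32 and 0.67, c without Intervention was 0.568 at OR 0.6 against 0.565 at OR 0.9.
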